1.0 INTRODUCTION

This document contains the statistical analysis plan for the Analyze ST IDE study using St. Jude Medical ICD systems. The Analyze ST study will include the following device models:

- Fortify[®] ST family of devices
- Fortify Assura[®] St family of devices
- Ellipse[®] family of devices

These devices will be collectively referred to as the Investigational Devices except where otherwise specified. All analyses will be carried out on the study endpoints as well as on additional data specified in this document.

2.0 PURPOSE

The intent of this study is to demonstrate the safety and effectiveness of the diagnostic ST Monitoring Feature in the Investigational Devices. Effectiveness of the device will be evaluated by analyzing the sensitivity of the ST Monitoring Feature to detect clinical events. In addition, safety of the ST Monitoring Feature will be evaluated by demonstrating a low percentage of patients with false positive events.

3.0 INVESTIGATIONAL PLAN

3.1 Study Design and Patient Follow-up

This is a prospective, non-randomized, multicenter, pivotal IDE study evaluating the Investigational Devices with the ST Monitoring Feature. The Analyze ST study is designed to demonstrate the safety and efficacy of the ST Monitoring Feature in the Investigational Devices. The sensitivity of the ST Monitoring Feature for detecting acute coronary syndrome events will be the primary efficacy endpoint. The primary safety endpoint will be assessed by reporting the percentage of patients who experience a false positive detection during the 12 months following a 3 month run-in period.

The goal of the 3 month run-in period is to:

1. Identify patients whose EGM rhythm or morphology is unsuitable for chronic ST monitoring
2. Provide data collection for review in order to adjust or optimize ST feature parameters

[figure not shown]
Data collection for the purposes of the FDA market approval application will be considered to be complete when the primary safety endpoint data are available and at least 41 clinical events have occurred. It is estimated that up to 5,228 patients at

Statistical Analysis Plan

approximately 200 centers will be enrolled in the study with a follow up of 12 months to meet the primary study endpoints.

A flow diagram of the study design is below.

Study Flow Diagram

3.2 Clinical Event Description and CEC Adjudication

Three types of events are defined in the sections below. All clinical events will be adjudicated by a Clinical Events Committee (CEC) consisting of a blinded panel of independent experts. Once the CEC adjudicates the Clinical Events, and per defined criteria in section 3.2.2, all Type I ST episodes will be classified as either False Positive or True Positive events. In addition, any Clinical Event that was not associated with a Type I ST episode detection will be classified as either False Negative or True Negative.

3.2.1 Clinical Event Committee

The CEC will include at a minimum, 2 interventional cardiologists and 2 electrophysiologists. Physicians on the CEC will not participate in the study as investigators and when reviewing events will be blinded to any patient or site information. The purpose of the CEC is to adjudicate all clinical events. Specifically:

- Classify clinical events as either an Acute Coronary Syndrome (ACS) Event, a Precursor Event, or a Non Event. Non Events will be further classified as either a Transient Ischemic Event or a Non Ischemic Event. Review all deaths, and adverse events associated with diagnostic testing or procedures performed as a result of a Type I ST Episode Detection and determine relationship to system and/or procedure.
- Review all baseline surface ECGs to determine the presence or absence of any conduction abnormality.
- Review all complications and all cardiovascular related adverse events

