3.2.2 Clinical Events

ACS Events

An ACS event is defined as any of the following:

- Death due to a myocardial infarction
- A new Q-wave myocardial infarction on 12-lead ECG
- ST elevation myocardial infarction
- Biomarker evidence of acute myocardial damage*
- Evidence of new plaque rupture by invasive testing (i.e., IVUS) as adjudicated by the blinded Clinical Events Committee
- The presence of TIMI myocardial perfusion grade 0 or 1 consistent with acute injury of the myocardium from embolization
- New surface ECG ST depression or elevation treated with thrombolytic medication

Statistical Analysis Plan

- New surface ECG ST depression or elevation with new or progressive flow-limiting ischemia proven by non-invasive or invasive testing.
- Angiographic stenosis $\geq 70\%$ adjudicated by the blinded Clinical Events Committee as flow-limiting.
- An event that leads to a clinically warranted percutaneous coronary intervention (PCI) or revascularization as determined by the blinded Clinical Events Committee. Clinically warranted is defined as:
 - Angiographically visualized stenosis $\geq 70\%$ correlating with the vascular distribution in which a 12-lead surface ECG documents changes consistent with ischemia or injury in 2 or more contiguous leads
 - Angiographically visualized stenosis $\geq 70\%$ correlating with a vascular distribution shown to have ongoing ischemia by non-invasive stress testing
 - New or progressive angiographically visualized stenosis $\geq 70\%$ correlated with new or progressive anginal symptoms

*NOTE: It is recommended that the “Universal Definition of Myocardial Infarction” proposed by the Joint ESC/ACCF/AHA/WHF in 2007 be used to determine myocardial damage.

Precursor Events

A precursor event is defined as clinical symptoms of an impending ACS event followed by an ACS event within 10 days. Precursor events alone do not meet the ACS event criteria. Multiple precursor events may precede a single ACS. All precursor events will be adjudicated by the Clinical Event Committee (CEC). Symptoms identified as precursors will be grouped with the subsequent ACS event and counted as a single event. Individual precursor events will not be included in the statistical endpoint analysis.

Non Events

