3.2.3 Classification of Events

True Positive (TP): A Type I ST episode detection that occurs up to 72 hours prior to an ACS Event.

False Positive (FP): A Type I ST episode detection that occurs more than 72 hours prior to an ACS Event or that occurs in the absence of a true ACS Event.

True Negative (TN): Absence of a Type I ST episode detection during a Non Event.

False Negative (FN): Absence of a Type I ST episode detection within 72 hours prior to an ACS Event.

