4.7.8 CPK Isoenzymes MB Fractions and Troponin

Cardiac biomarker laboratory tests will be collected during any clinical event as defined by the study protocol. Results will be determined as positive or negative and will be compared to clinical events and to Type I ST episodes.

4.7.9 12-Lead ECG Measurements

12-lead ECG recordings will be collected at the Baseline visit and during any clinically-indicated stress test related to Clinical Events. Results from the 12-lead ECG recordings along with the patient's pertinent medical records will be adjudicated by the CEC and classified as normal or abnormal. All ECG abnormalities will be classified as a preexisting abnormality or as a new finding. An abnormal 12-Lead ECG is defined as having at least one of the following present 1) rhythm other than normal sinus rhythm or sinus tachycardia such as atrial fibrillation, atrial flutter, supraventricular tachycardia, ventricular tachycardia, or idioventricular rhythm 2) intermittent or complete conduction abnormalities resulting in widening of the QRS complex (RBBB, LBBB, IVCD, evidence of left ventricular hypertrophy), 3) ST-T wave abnormalities (T wave inversions, J point elevation) 4) frequent PVCs 5) low voltage QRS complexes indicative of dilated cardiomyopathy or COPD, or 6) high voltage QRS complexes indicative of left ventricular hypertrophy. A normal 12-Lead ECG will be defined as one not meeting the criteria for an abnormal ECG.

Results of any stress tests performed will be determined as positive or negative by the site and will be sent to the CEC for further adjudication

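### The plan calls the CEC blinded but never says the blind covers ST detections, so the ACS decision behind both primary endpoints is open to review bias

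*Protocol*

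**What the plan says.** Section numbers below are the same in the Protocol and the SAP, which carry the same text on this point.

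- **The blind.** Section 3.2 states: "All clinical events will be adjudicated by a Clinical Events Committee (CEC) consisting of a blinded panel of independent experts". The bare word blinded recurs in 3.2.2 and 4.3.1. Only 3.2.1 says to what: members "when reviewing events will be blinded to any patient or site information".
- **The CEC's tasks.** Section 3.2.1 tells the committee to "Classify clinical events as either an Acute Coronary Syndrome (ACS) Event, a Precursor Event, or a Non Event". The same bullet has it review deaths and "adverse events associated with diagnostic testing or procedures performed as a result of a Type I ST Episode Detection", and judge their relationship to the system or procedure.
- **Judgement in the ACS definition.** Section 3.2.2 lists criteria of which any one suffices. One is a stenosis of at least 70% "adjudicated by the blinded Clinical Events Committee as flow-limiting". Plaque rupture on invasive testing and clinically warranted revascularization are also left to the committee.
- **Order of steps.** Section 3.2: "Once the CEC adjudicates the Clinical Events, and per defined criteria in section 3.2.2, all Type I ST episodes will be classified" as true or false positive.
- **What is scored.** Section 3.2.3 defines a true positive as "A Type I ST episode detection that occurs up to 72 hours prior to an ACS Event". Section 4.4.1 takes sensitivity as true positives over ACS events and requires the lower 95% Wilson bound to exceed 50%.

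**The concern.** In a study of diagnostic sensitivity, the reference standard has to be set without knowledge of the test result. Here the test is the Type I ST detection and the reference standard is the CEC's ACS decision. A blind to patient and site does not plainly include the detection, its time, the Patient Notifier or Merlin.net alert, or the stored electrogram.

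If committee members know that the device alarmed, a borderline event with an alarm is more easily called ACS, which turns a false positive into a true positive. A borderline event without an alarm is more easily called a Non Event, which turns a false negative into a true negative. Both shifts raise sensitivity. The first also lowers the primary safety percentage, for patients with no other false positive. Both primary endpoints would move in the device's favour, and no later analysis can undo a biased reference standard.

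**Working it through.** **1. Does any text withhold the detection?**

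| Section | What it says | Covers alarm status? |
|---|---|---|
| 3.2, 3.2.2, 4.3.1 | Committee is blinded | No object named |
| 3.2.1 | Blind to patient or site information | Not listed |
| 3.2 | Episodes labelled after adjudication | Sequence only |
| 3.2.1 | Reviews adverse events of detection-prompted tests and procedures | Task reveals the alarm; not separated in time from classification |

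None does.

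**2. The plan's figure.** Sections 3.1 and 4.5 of the Protocol require at least 41 clinical events. The assumed sensitivity and power are redacted, so 41 cannot be formally reproduced. It is compatible with several pairs, for example 74% sensitivity with a 90% power target (exact power at 41 events: 91.1%). No error in 41 is alleged. I read the 41 as ACS events, which is an assumption.

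**3. The success threshold at n = 41.** With z = 1.96, the Wilson lower bound is

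[p + z²/(2n) − z·√(p(1−p)/n + z²/(4n²))] / (1 + z²/n).

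- 26/41 gives 48.1%: fails.
- 27/41 gives 50.5%: passes.
- Exact type I error at true sensitivity 50%: P(X ≥ 27) = 2.98%.

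With the count held at 41, one event more or fewer in the true positive column decides the result. If upgraded alarmed events add to the denominator instead, 27/42 still fails (49.2%) and 28/43 passes (50.2%), so two are needed.

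**4. Bias scenarios (all rates assumed).** Let b be the borderline share of candidate events, with half of all candidates alarmed. Clear cases are always called ACS. Masked reviewers accept half of borderline cases; unmasked reviewers accept 0.5 + d of those with an alarm and 0.5 − d of those without. Then

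observed sensitivity = [(1−b)·0.5 + b·0.5·(0.5+d)] / [(1−b) + b·0.5].

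With d = 0 this returns 50%.

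| Acceptance with / without alarm | b | Observed sensitivity | P(X ≥ 27 of 41) |
|---|---|---|---|
| 65% / 35% | 10% | 0.4825/0.95 = 50.8% | 3.7% |
| 65% / 35% | 30% | 0.4475/0.85 = 52.6% | 6.1% |
| 75% / 25% | 10% | 0.4875/0.95 = 51.3% | 4.3% |
| 75% / 25% | 20% | 0.4750/0.90 = 52.8% | 6.3% |
| 75% / 25% | 30% | 0.4625/0.85 = 54.4% | 9.3% |

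**5. Cross-check with a second model.** Let u be the number of alarmed Non Events upgraded per true ACS event, so observed sensitivity = (0.5 + u)/(1 + u). For u = 0.05, 0.10 and 0.20 this gives 52.4%, 54.5% and 58.3%, with false-success probabilities of 5.7%, 9.6% and 20.8%. The answer depends on the assumed rate, and the documents do not supply one.

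**The case against.** The sponsor can fairly say that the panel is called independent and blinded throughout, including beside the judgement-based criteria; that a blind to patient information can be read to include device data; and that episodes are labelled only after adjudication. The alarm-linked task concerns adverse events, not ACS classification. Death from MI, Q-wave MI, STEMI and biomarker criteria leave little room for judgement, and clinically warranted is itself tied to stenosis of at least 70% with ECG, stress-test or symptom correlation. The file labelled Protocol is itself SAP text and refers to a separate investigational protocol; that document or a CEC charter could set out the masking.

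Most of this stands as a limit on the point. It rules out three stronger readings that a reader might infer:

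- **That the CEC was unmasked.** The documents are silent on alarm status; they do not say it was disclosed. Exposure during ACS classification is an inference from one committee doing both tasks.
- **That the plan contradicts itself by giving a blinded committee medical records.** Section 4.7.9 says "Results from the 12-lead ECG recordings along with the patient's pertinent medical records will be adjudicated by the CEC", but the task there is to classify ECGs as normal or abnormal, and de-identified records are an ordinary reading of the 3.2.1 blind. Nothing states what the records say about alarms.
- **That ACS onset times follow the alarm.** The 72-hour window makes onset time matter, but no section says who sets it or with what knowledge. This is silence, not evidence of a biased rule.

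What the objection does not supply is a sentence that withholds the detection. A sequence does not stop a member who has seen the alarm from being influenced by it, and each judgement-based criterion is sufficient alone.

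**Conclusion.** The point holds as a gap in the blinding rule. The stated scope omits the index test, and nothing else in the two documents fills the gap, so the rule can be followed to the letter while ACS status is decided with knowledge of the alarm. Any resulting bias would favour the device on both primary endpoints.

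The size is unknown. At 41 ACS events and true sensitivity 50%, with 10% to 30% borderline cases and acceptance shifted to 65/35 or 75/25, false success rises from 3.0% to between 3.7% and 9.3%. At the low end the effect is small. These are illustrations, and the effect on the false positive percentage cannot be sized from the documents. Importance is moderate, as is confidence, because the investigational protocol and any charter were not available.

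**What to change.** Amend 3.2.1 in both documents, and the CEC charter to match:

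1. When it classifies an event as ACS, Precursor or Non Event, the CEC is blinded to patient identity, site and all ST-feature data: detections, times, alerts, electrograms and references to them in source records.
2. The ACS onset date and time are fixed under the same masking, by a named role.
3. Both decisions are locked before any episode data are released.
4. The Type I episode log is matched to the locked events by program to assign TP, FP, FN and TN under 3.2.3.
5. Only then does the CEC receive alarm-linked material to judge complications and relatedness.

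If a charter already does this, it is enough to cite it and bring the 3.2.1 wording into line. The cost is wording changes and redaction of event packets, with no new committee or patient procedure. Masking may be imperfect in narrative records.

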3.2.2 Clinical Events

ACS Events

An ACS event is defined as any of the following:

- Death due to a myocardial infarction
- A new Q-wave myocardial infarction on 12-lead ECG
- ST elevation myocardial infarction
- Biomarker evidence of acute myocardial damage*
- Evidence of new plaque rupture by invasive testing (i.e., IVUS) as adjudicated by the blinded Clinical Events Committee
- The presence of TIMI myocardial perfusion grade 0 or 1 consistent with acute injury of the myocardium from embolization
- New surface ECG ST depression or elevation treated with thrombolytic medication

Statistical Analysis Plan

- New surface ECG ST depression or elevation with new or progressive flow-limiting ischemia proven by non-invasive or invasive testing.
- Angiographic stenosis $\geq 70\%$ adjudicated by the blinded Clinical Events Committee as flow-limiting.
- An event that leads to a clinically warranted percutaneous coronary intervention (PCI) or revascularization as determined by the blinded Clinical Events Committee. Clinically warranted is defined as:
 - Angiographically visualized stenosis $\geq 70\%$ correlating with the vascular distribution in which a 12-lead surface ECG documents changes consistent with ischemia or injury in 2 or more contiguous leads
 - Angiographically visualized stenosis $\geq 70\%$ correlating with a vascular distribution shown to have ongoing ischemia by non-invasive stress testing
 - New or progressive angiographically visualized stenosis $\geq 70\%$ correlated with new or progressive anginal symptoms

*NOTE: It is recommended that the “Universal Definition of Myocardial Infarction” proposed by the Joint ESC/ACCF/AHA/WHF in 2007 be used to determine myocardial damage.

Precursor Events

A precursor event is defined as clinical symptoms of an impending ACS event followed by an ACS event within 10 days. Precursor events alone do not meet the ACS event criteria. Multiple precursor events may precede a single ACS. All precursor events will be adjudicated by the Clinical Event Committee (CEC). Symptoms identified as precursors will be grouped with the subsequent ACS event and counted as a single event. Individual precursor events will not be included in the statistical endpoint analysis.

Non Events

Non Events are defined as any clinical event that does not meet the criteria of an ACS Event or a Precursor Event. These events will be adjudicated by the CEC and will be further classified as either Transient Ischemic Events or as Non Ischemic Events.

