4.3.2 Primary Safety Endpoint

The ST Monitoring Feature will be evaluated by the percentage of patients with false positive events. The percentage of patients with false positive events is calculated as the number of patients who experience false positives divided by the number of evaluable patients. A False Positive occurs when a clinical event does not occur within 72 hours following a Type I ST episode.

The hypothesis is formally expressed as follows:

H_0 : Percent of patients experiencing a false positive event in 12 months $\geq 15\%$

H_a : Percent of patients experiencing a false positive event in 12 months $< 15\%$

The desired outcome is to reject the null hypothesis at the 2.5% significance level. The null hypothesis will be rejected at the 2.5% significance level if the

Statistical Analysis Plan

upper bound of the 95% confidence interval for the percent of patients experiencing false positive events is less than 15%. The upper confidence bound will be calculated using the Wilson score interval method.

Patient Group

All enrolled patients who have a successful implant or system revision, complete the baseline follow up visit and have the ST Monitoring Feature and Patient Notifier turned ON will be included in the evaluation of this study endpoint. Data collection towards the study endpoint will begin after the Baseline visit.

Further, the analysis population for the primary safety endpoint will be those subjects with the Fortify[®] ST (upgraded), Fortify Assura[®] ST and Ellipse[®] ST. Data from subjects with a Fortify[®] ST device prior to being upgraded will not be included in this analysis.

Analysis

Primary Analysis

The primary analysis will be a complete case analysis where patients who are lost to follow-up before completing their 12 month visit without experiencing a false positive event will be considered non-evaluable and omitted from the analysis of the endpoint. Patients experiencing a false positive event and withdrawing before the 12 month visit will be included in the analysis. The proportion of patients experiencing false positives will be estimated by the number of patients experiencing a false positive event divided by the number of evaluable patients.

Imputation Analysis

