3.2.3 Classification of Events

True Positive (TP): A Type I ST episode detection that occurs up to 72 hours prior to an ACS Event.

False Positive (FP): A Type I ST episode detection that occurs more than 72 hours prior to an ACS Event or that occurs in the absence of a true ACS Event.

True Negative (TN): Absence of a Type I ST episode detection during a Non Event.

False Negative (FN): Absence of a Type I ST episode detection within 72 hours prior to an ACS Event.

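### The false positive rule refers to an ACS Event in section 3.2.3 but to any clinical event in sections 4.3.2 and 4.3.3, so an alarm followed by a precursor can get opposite scores

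*Protocol*

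**What the plan says.** The Protocol and the SAP carry the same text in these sections.

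- **Section 3.2** requires every Type I ST episode to be classified as either a true or a false positive.
- **Section 3.2.1** has the Clinical Events Committee (CEC) sort clinical events into ACS Events, Precursor Events and Non Events.
- **Section 3.2.2** gives the precursor rules. The definition is: "A precursor event is defined as clinical symptoms of an impending ACS event followed by an ACS event within 10 days". A precursor does not qualify by itself: "Precursor events alone do not meet the ACS event criteria". The counting rule is: "Symptoms identified as precursors will be grouped with the subsequent ACS event and counted as a single event". For the analysis, the section adds: "Individual precursor events will not be included in the statistical endpoint analysis". It gives no onset time for the grouped event.
- **Section 3.2.3** times everything against the ACS event. A true positive is "A Type I ST episode detection that occurs up to 72 hours prior to an ACS Event". A false positive is "A Type I ST episode detection that occurs more than 72 hours prior to an ACS Event", or one with no ACS event at all. On the event side: "False Negative (FN): Absence of a Type I ST episode detection within 72 hours prior to an ACS Event".
- **Section 4.3.2** (primary safety) states a different rule: "A False Positive occurs when a clinical event does not occur within 72 hours following a Type I ST episode". Section 4.3.3 (secondary safety) is also keyed to a clinical event.
- **Section 4.4.1** (primary efficacy) takes true positives from 3.2.3, but adds a sentence that relates an episode to a clinical event within 72 hours.
- **Section 4.7.4** builds the positive predictive value (PPV) on 3.2.3 and treats true and false positives together as all Type I episodes.
- **Section 4.7.15** repeats the primary and secondary endpoints with a 14-day threshold, as an additional analysis.

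**The concern.** The false positive is what the primary and secondary safety endpoints count, and the plan defines it twice with different reference events. The definitions part company whenever an alarm is followed within 72 hours by a clinical event that is not an ACS event. Precursors make this concrete. They may precede the ACS event by up to 10 days, the 3.2.3 window is 72 hours, and 3.2.2 does not say whether the merged event begins at the first symptom or at the ACS event.

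Two programmers working from this text could count different patients in the primary safety endpoint. The sentence in 4.4.1 leaves a similar opening on the efficacy side. If the choice is made after alarms and adjudications are known, it can be made in the direction that helps.

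**Working it through.** **One record under each rule.** Take an alarm at hour 0, symptoms at hour 12, an ST elevation infarction at hour 144, and no other alarm. The symptoms precede the ACS event by 144 − 12 = 132 hours. That is within 10 days (240 hours), so the CEC can call them a precursor.

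| Rule | Reference event | Time from alarm | Score |
|---|---|---|---|
| 3.2.3, the alarm | ACS Event | 144 h > 72 h | false positive |
| 4.3.2 and 4.3.3, the alarm | clinical event (the precursor) | 12 h ≤ 72 h | not a false positive |
| 3.2.3, the ACS event | alarm in the preceding 72 h | none in hours 72 to 144 | false negative |

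Under 4.3.2 the alarm is not a false positive, and under 3.2.3 it is not a true positive. It then has no class, contrary to 3.2, and the identity used in 4.7.4 fails. A further alarm between hours 72 and 144 would make the ACS event detected; only the first alarm would stay in dispute. With the infarction at hour 60, the first alarm is a true positive under 3.2.3 and not a false positive under 4.3.2, so the rules agree.

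**Where the precursor conflict can arise.** It needs alarm to precursor ≤ 72 h, precursor to ACS event ≤ 240 h, and alarm to ACS event > 72 h. The disputed alarms therefore lie between 72 h and 72 + 240 = 312 h (13 days) before the ACS event. The 14-day re-analysis (336 h) covers them all. Of the permitted precursor window, (240 − 72)/240 = 70% lies outside the 72 hours. This is a share of time, not of precursors.

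**Size for primary safety.** Assume 41 ACS events in 41 different patients, each with a disputed alarm and no other false positive, and all 5,228 patients evaluable. The shift is 41/5,228 = 0.8 points. The Wilson upper bound is below 15% when the observed proportion is below 0.15 − 1.96 × √(0.15 × 0.85/5,228) = 0.1403, that is, at most 733 patients (14.0%). A shift of 41 would reverse the result only if the 4.3.2 count lay between 693 and 733 (13.3% to 14.0%). If only half the patients were evaluable (2,614, an assumption), the shift would be 41/2,614 = 1.6 points. Data collection runs to at least 41 events, so these are guides rather than limits. They cover precursors only: an alarm followed within 72 hours by a Non Event is also scored differently by the two rules, and the documents give no count of Non Events.

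**Size for sensitivity.** The inputs behind the 41 events are blacked out, so that figure cannot be reproduced. I use it as the number of ACS events, although 4.5 also says clinical events. The Wilson lower bound, with p = x/n and z = 1.96, is

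(p + z²/2n − z√(p(1−p)/n + z²/4n²)) / (1 + z²/n).

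At n = 41 it is 48.1% for x = 26 and 50.5% for x = 27, so success needs 27. One reclassified event moves the estimate by 1/41 = 2.4 points. A result of 29/41 (lower bound 55.5%) passes; with three events moved to false negative it is 26/41 and fails.

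**The case against.** The strongest reply is that 3.2.2 and 3.2.3 are coherent together. Precursors alone are not ACS events and do not enter the endpoint analysis individually, so grouping is a counting rule that stops one ACS event from being counted several times. Nothing moves its onset back to the first symptom. I accept this, and the fix adopts it. It does not reconcile 4.3.2 and 4.3.3 with 3.2.3. The exclusion of individual precursors suggests that 3.2.3 was meant, but the endpoint sections use the broader term, and precursors are one of its classes.

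A reader might go further and infer that sensitivity is biased low, and that the primary true positive window should open at the first precursor. The documents do not support this. The defined target is detection within 72 hours before the ACS event, and a miss by that definition is not an error of estimation. The double penalty also needs two conditions: an alarm more than 72 hours before the ACS event, and no later alarm inside that window. The longer window would favour the device. A notified patient may seek care and have symptoms recorded, so a precursor may be recorded because of the alarm. Section 3.2.1 blinds the CEC to patient and site information and does not mention alarms.

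It can also be said that 4.7.15 already captures these alarms. It does, but it widens the window for every event, with or without a precursor, and it does not settle which false positive rule governs the primary safety test.

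**Conclusion.** The conflict is real and lies in an operative definition. For an alarm followed within 72 hours by a precursor or a Non Event, but by no ACS event in that time, 3.2.3 says false positive, while 4.3.2 and 4.3.3 say not. The broader wording lowers the false positive count and so favours the device on both safety endpoints.

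For precursors the effect on the primary safety percentage is small, about 0.8 points on the assumptions shown, and decisive only near 13% to 14%. For Non Events it cannot be bounded from the documents. For sensitivity, 3.2.3 read literally gives a definite answer; what is missing is an explicit statement that a grouped event is timed at the ACS event. Each event scored the other way is worth 2.4 points at 41 events, and how many would be affected is unknown. This should be settled before adjudicated results are seen. It does not justify replacing the 72-hour primary definition.

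**What to change.** 1. Use the 3.2.3 rule, with 72 hours and the ACS Event as the single reference, in 4.3.2, 4.3.3, 4.4.1 and 4.7.4.
2. State in 3.2.2 and 3.2.3 that a grouped precursor and ACS event is timed at the ACS event.
3. Keep the strict 72 hours as the primary analysis.
4. Beside the 14-day re-analysis in 4.7.15, add a named supportive analysis that times grouped events from the first CEC-adjudicated precursor. The CEC should date the precursor without sight of alarms, and each ACS event should contribute at most one true positive. Report how many events change score.

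The cost is SAP wording, one CEC date field, and a procedure that keeps alarm data from the CEC while it dates precursors. The false positive percentage may become slightly less favourable than under the 4.3.2 wording; any part due to Non Events cannot be sized from the documents.
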